6.8. Product Accountability

An accurate and current accounting of the dispensing and return of IMP(s) will be maintained on an ongoing basis by the pharmacist and a member of the study site staff in the Accountability Log and case report form and will be verified by the study's monitor.

6.9. Prior and Concomitant Medication

6.9.1. Allowed concomitant treatment

Are allowed all medications related to patient's current affection (i.e. medical history).

This study aims to enroll patients that are newly diagnosed with COVID-19, without sign of respiratory distress.

The standard of care in non-hospitalized patients, according the WHO recommendations, consists mainly of symptomatic treatments and antibiotic therapies as appropriate at the physician's discretion. The use of concomitant medications will be recorded in the eCRF.

The standard of care in hospitalized patients may vary between sites and depends upon patient status and will remain at the physician's discretion.

Concomitant treatment with either corticosteroids (e.g. dexamethasone) or remdesivir is allowed providing they are part of a Standard of Care duly authorized in the respective countries where the study is conducted.

6.9.2. Prohibited concurrent medications

The following drugs are prohibited at enrollment and during the study:

- all immunosuppressor or immunomodulator agents (cf. appendix #2)
- Use of any investigational or non-registered product within 3 months or within 5 half-lives before enrollment, whichever is longer.

The following drugs are prohibited during the study:

- Drugs that could interact with ABX464 should be avoided especially the CYP1A2 substrates (cf. Appendix #1). The following CYP1A2 substrates with a narrow therapeutic margin are prohibited during the whole course of the study (clozapine, theophylline, ropinirol, warfarin and methadone). In case of concomitant treatment with ondansetron the maximal daily dose must be limited to 8 mg.
- Inhibitors or inducers of the CYP1A2 (cf. Appendix #1).

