5. Women of childbearing potential and men receiving the study treatment and their partners must agree to use a highly effective contraceptive method during the study and for 6 months (180 days) after end of study or early termination. Contraception should be in place at least 2 weeks prior to enrolment. Women must be surgically sterile or if of childbearing potential must use a highly effective contraceptive method. Women of childbearing potential (WOCBP) will enter the study after confirmed menstrual period and a negative pregnancy test. Highly effective methods of contraception include true abstinence, intrauterine device (IUD) or hormonal contraception aiming at inhibition of ovulation, intrauterine hormone releasing system, bilateral tubal ligation, vasectomized partner. True abstinence is defined when this is in line with the preferred and usual lifestyle of the patient. In each case of delayed menstrual period (over one month between menstruations) confirmation of absence of pregnancy is required. This recommendation also applies to WOCBP with infrequent or irregular menstrual cycle. Female and male patients must not be planning pregnancy during the trial and for 6 months post completion of their participation in the trial. In addition, male patients should use condom during the trial and for 6 months (180 days) post completion of their participation in the study. Male patients must not donate sperm as long as contraception is required. *For the purpose of this protocol, a woman is considered of childbearing potential (WOCBP), i.e. fertile, following menarche and until becoming post-menopausal unless permanently sterile. Permanent sterilisation methods include hysterectomy, bilateral salpingectomy and bilateral oophorectomy. A postmenopausal state is defined as no menses for 12 months without an alternative medical cause. A high follicle stimulating hormone (FSH) level in the postmenopausal range may be used to confirm a*

post-menopausal state in women not using hormonal contraception or hormonal replacement therapy. However, in the absence of 12 months of amenorrhea, a single FSH measurement is insufficient. Finally, a man is considered fertile after puberty unless permanently sterile by bilateral orchidectomy.

6. Patients must understand, sign and date the written voluntary informed consent form at the visit prior to any protocol-specific procedures.
7. Patients able and willing to comply with study visits and procedures as per protocol.

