8. Patients should be affiliated to a social security regimen (for French sites only).

4.2.2.Exclusion Criteria

Patients who meet any of the following exclusion criteria will be excluded from the study:

1. Patients with moderate or severe acute respiratory failure or requiring non-invasive ventilation or oxygen or with SpO₂ < 92% or tachypnea (respiratory rate ≥ 30 breaths/min).
2. Patients treated with immunosuppressors and/or immunomodulators (cf. Appendix #2).
3. Engrafted patients (organ and/or hematopoietic stem cells).
4. Patients with uncontrolled auto-immune disease.
5. Patients with known or suspected active (i.e. not controlled) bacterial, viral (excluding COVID-19) or fungal infections.
6. Patients with preexisting, severe and not controlled organ failure.
7. History or active malignancy requiring chemotherapy or radiation therapy (excluding 2 years disease free survivor patients).
8. Pregnant or breast-feeding women.
9. Illicit drug or alcohol abuse or dependence that may compromise the patient's safety or adherence to the study protocol.
10. Use of any investigational or non-registered product within 3 months or within 5 half-lives preceding baseline, whichever is longer.
11. Hypersensitivity to ABX464 and/or its excipients.
12. Any condition, which in the opinion of the investigator, could compromise the patient's safety or adherence to the study protocol.

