¹ **Physical examinations:** a complete physical examination will be performed at D0, at the End of treatment visit (EoT), and at D48. Only differences from baseline will be reported at every other visit

² **Body Weight and Height:** Body weight and height will be measured at D0 for BMI assessment.

³ **ECG:** A 12-Leads ECG will be performed at every on-site study visit.

⁴ **Blood pregnancy test:** Applicable to all women of childbearing potential at D0 and at D48. In order not to limit the patient enrollment a urine pregnancy test can be performed in addition if the blood test result is not available at the time of randomization.

⁵ **Hematology + Biochemistry:** samples to be taken at every on-site study visit (except D7 for outpatients if not possible) and analyzed locally.

⁶ **CRP, Troponin I & T and D-Dimer:** samples to be taken at every on-site study visit (except D7 for outpatients if not possible) and sent to central laboratory for biobanking purpose.

⁷ **Immunophenotyping and cells activation markers:** samples will be taken in selected sites and for approximately 100 patients.

⁸ **Blood sample Cytokines:** samples will be taken in all sites for all patients.

⁹ **Chest CT-scan:** procedure concerns hospitalized patients only (whenever the hospitalization occurs during the course of the study). Images taken at discharge (\pm 7 days) will be assessed locally, then collected and sent to a blinded central reader for descriptive analysis of the lesions. If available at D0, Baseline CT scans of hospitalized patients will be sent to Central Reader for comparison purpose.

¹⁰ **Respiratory function evaluation:** This evaluation will be performed only in patients who were hospitalized during the course of the study. For these patients the MRC Dyspnea assessment scale must be used at discharge and 3 months after last study drug intake. For sites having adequate facilities a PFT (FEV₁ and slow and forced Vital Capacity) and a Carbon Monoxide Diffusing Capacity (CMDC) evaluation will be performed at discharge and 3 months after last study drug intake (optional assessments). For this last test, a blood sample for hemoglobin assessment must be taken within 48hrs prior to the CMDC test.

¹¹ **ABX464/placebo treatment dispensation:** treatment dispensation will be allowed once all the selection criteria are confirmed, including laboratory assessments for patients' eligibility confirmation.

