6.4. Method of assigning patients to treatment arms

All patients will be assigned a unique and incremental Patient Identification (ID) number. Patient IDs will be unique (i.e. reallocation of the ID will not be permitted). The format will be a seven-digit number as follows: site number (4 digits) – Patient number (3 digits). The latter 3-digit Patient number will be assigned according to the patient's order of inclusion in the center.

Eligible patients (i.e. those who fulfil all inclusion/exclusion criteria) will be randomized across the study according to a 2:1 ratio to ABX464 50mg : placebo treatment arms.

Patients will be stratified according to:

- Age \geq 65 years or $<$ 65 years (with at least one risk factor)
- Inpatient or outpatient, at the time of enrolment

Randomization will be performed via IWRS. Treatment numbers will be allocated as per randomization list.

In all cases at the end of treatment visit, all patient should return the bottle dispensed at D0 for a compliance check.

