7.2. Patient Premature trial discontinuation

A patient can be withdrawn at any time from the study. Premature trial discontinuation could occur for the following reasons:

- Investigator's decision.
- An Adverse Event or an intercurrent condition that preclude continuation of treatment. Specifically, an elevation $\geq 3.0 \times$ ULN in liver transaminases (AST/SGOT and/or ALT/SGPT) or Alkaline phosphatase or in total bilirubin compared to baseline requires close observation with repeating liver enzymes and serum bilirubin tests every 2 days. Discontinuation of the study treatment should occur if:
 - ALT or AST $> 8 \times$ ULN
 - ALT or AST $> 3 \times$ ULN and total bilirubin $> 2 \times$ ULN or INR > 1.5
 - ALT or AST $> 3 \times$ ULN with appearance of fatigue, nausea, vomiting, right upper quadrant pain or tenderness, fever, rash, and/or eosinophilia ($> 5\%$).
 - Alkaline Phosphatase $\geq 2.0 \times$ ULN
- Serious adverse event with suspected causal relationship to the IMP
- Any relevant toxicity or negative change in the risk/benefit assessment leading to an unacceptable risk for the patient (i.e. occurrence of adverse events which character, severity or frequency is new in comparison to the existing risk profile), or any data deriving from other clinical trials or toxicological studies which negatively influence the risk/benefit assessment.
- Major protocol violation.
- Withdrawal of consent.
- Administrative reasons from Sponsor.

A patient who prematurely exits the study will not be replaced.

All patients, regardless of the completion or premature discontinuation, should come back for an on-site safety follow-up visit 21 days after the last study drug intake, and all examinations must be performed according to the study flow-chart.

The same long-term follow-up will be performed as described in section 7.1 providing the reason for premature discontinuation is not "withdrawal of consent".

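### Section 6.9.2 prohibits five narrow-margin CYP1A2 substrates and the Appendix 1 inhibitors and inducers, but no eligibility criterion names them, and inclusion 5 accepts contraception that Appendix 1 can prohibit

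*Protocol*

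**What the plan says.** Section 6.9.2 of the protocol has two lists. The first opens with "The following drugs are prohibited at enrollment and during the study" and covers immunosuppressors, immunomodulators and investigational products. The second opens with "The following drugs are prohibited during the study" and covers the CYP1A2 drugs. Within the second list, "The following CYP1A2 substrates with a narrow therapeutic margin are prohibited during the whole course of the study (clozapine, theophylline, ropinirol, warfarin and methadone". Inhibitors and inducers of CYP1A2 are prohibited by reference to Appendix 1, whose inhibitor list includes ethinyl estradiol.

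On entry, section 6.4 says "Eligible patients (i.e. those who fulfil all inclusion/exclusion criteria) will be randomized across the study". Footnote 11 of the flow chart (5.1) says that "treatment dispensation will be allowed once all the selection criteria are confirmed". Two general criteria bear on the question. Inclusion 7 asks for "Patients able and willing to comply with study visits and procedures as per protocol". Exclusion 12 (section 4.2.2) covers "Any condition, which in the opinion of the investigator, could compromise the patient's safety or adherence to the study protocol".

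Inclusion 5 lists ovulation-inhibiting hormonal contraception among its highly effective methods and says that contraception should be in place for at least 2 weeks before enrolment.

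On timing, section 3.5 says that there is no screening visit, and section 3.1 says that the first dose should follow the diagnostic test by no more than 48 hours. Section 5.2.1 has all current medication recorded at Day 0 and the first dose taken on site. Section 9.1.1 classes intake of a 6.9.2 drug as a major deviation.

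**The concern.** The trial seeks out older patients and those with diabetes, hypertension, obesity or ischaemic cardiovascular disease, so long-term medication at entry is foreseeable. A patient established on warfarin, methadone or another listed drug can meet every criterion that names something specific. The site then has about two days, with no guidance, to decide between three courses: refuse the patient on its own judgement, stop or switch a drug that the protocol itself describes as having a narrow margin, or give the first dose and incur a major deviation. With about 75 sites (section 4.1), the same patient could be handled differently in different places.

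Contraception adds a second risk. Section 1.5 reports a rabbit embryo-fetal no-adverse-effect level below 1 mg/kg, so a woman should not be left without effective contraception because two sections of the protocol disagree about her product.

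**Working it through.** No sample size, power or alpha figure enters this point. The check sets the prohibitions beside the criteria and then follows a patient through Visit 1.

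**1. Prohibitions against criteria (6.9.2 and Appendices 1 and 2 against 4.2.1 and 4.2.2)**

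| Prohibited in 6.9.2 | Criterion that names it |
|---|---|
| Immunosuppressors and immunomodulators (Appendix 2) | Exclusion 2 |
| Investigational or non-registered products | Exclusion 10 |
| Five narrow-margin CYP1A2 substrates | None |
| CYP1A2 inhibitors and inducers (Appendix 1) | None, except teriflunomide, which is also in Appendix 2 |

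Criteria that name the five substrates, CYP1A2 or Appendix 1: 0 of 8 inclusion + 0 of 12 exclusion = 0 of 20. The synopsis has the same gap.

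**2. How many drugs**

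Appendix 1 says that bold type marks the prohibited drugs. In the copy reviewed, 8 of the 10 listed inhibitors are bold and none of the 5 inducers is; bold type may have been lost in conversion.

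- Bold entries only: 5 substrates + 8 inhibitors = 13 drugs.
- Plain wording of 6.9.2, which covers inhibitors and inducers generally: 5 + 10 + 5 = 20 drugs, or 19 once teriflunomide is set aside.

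The five substrates are named in 6.9.2 itself. Ethinyl estradiol is a listed inhibitor, so it is prohibited on either reading.

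**3. A patient already on one of the five substrates**

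- The drug is recorded at Day 0 (5.2.1), but no criterion requires that record to be checked against 6.9.2 before randomisation.
- Exclusions 2 and 10 do not apply. Exclusion 12 applies only if the investigator so judges.
- The time available is at most 48 hours from test to first dose. Visit 1 may be split, but by no more than 48 hours. No stop, switch or washout rule is given.
- If the drug continues, the first dose brings a major deviation under 9.1.1. A major violation is then a ground for discontinuation. Section 7.2 is permissive ("Premature trial discontinuation could occur for the following reasons"); the synopsis makes it mandatory.

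**4. A woman relying only on an ethinyl-estradiol contraceptive**

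Inclusion 5 lists 6 methods: true abstinence, intrauterine device, ovulation-inhibiting hormonal contraception, intrauterine hormone system, tubal ligation and a vasectomised partner. Only the ovulation-inhibiting method can conflict, and only if the product contains ethinyl estradiol (6 − 1 = 5 methods raise no conflict).

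If she keeps the product, she meets inclusion 5 and breaches 6.9.2. If she stops it after diagnosis, a newly started replacement has at most 2 days in place before the first dose, against the 14 days that inclusion 5 expects: a shortfall of at least 14 − 2 = 12 days.

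**The case against.** The strongest reply is that the prohibition is already in force. Section 6.9.2 bans the five substrates for the whole study, section 8.1.1 dates enrolment to signature of the consent form, and current medication is recorded at that visit. A first dose given on top of warfarin would then be a site failing to follow an express rule. This stands. A reader might infer that randomisation and dispensing depend on the listed criteria alone, so that the protocol permits such a patient. The documents do not support that: sections 6.4 and 5.1 require the criteria to be met, but neither suspends 6.9.2.

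A reader might also infer from the two opening lines of 6.9.2 that CYP1A2 drugs were deliberately allowed at enrolment. That is not supported either. The synopsis puts all the prohibited drugs under one heading without the contrast.

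Exclusion 12 can fairly be read to cover a patient who depends on a prohibited drug, since 6.9.2 is part of the protocol to be adhered to. It permits refusal but does not require it, and it depends on each investigator's opinion. Inclusion 7 is weaker, because it speaks of visits and procedures.

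Placing interaction bans in the medication section instead of among the exclusions can be a legitimate drafting choice. It works less well here, with no screening period and no stop or switch rule. The contraception conflict is indeed narrow, but it is a direct mismatch between two sections.

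**Conclusion.** The point holds as a gap between the medication rules and the eligibility criteria. The protocol prohibits these drugs but gives sites no named criterion with which to identify patients already taking them, and no instruction for the 48 hours before the first dose. In one case, ethinyl estradiol, a criterion accepts what Appendix 1 prohibits.

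What the documents fix is 0 of 20 criteria, 13 to 20 prohibited drugs depending on how Appendix 1 is read, and 1 of 6 contraceptive methods. They give no prevalence of use, so the number of patients affected is unknown and none is claimed. The contraceptive point assumes that some ovulation-inhibiting products contain ethinyl estradiol and that the woman has no other qualifying method.

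A reader might infer harm to the trial's results. The documents do not support that. The full analysis set keeps every randomised patient, and the 78% power does not depend on this rule. SAP version 5.0 has no efficacy analysis and no per-protocol set. At most, such a patient could appear in the SAP's summary of major deviations (4.5.2) or be flagged in the medication listing (4.8). The gain from correction is patient safety and uniform handling across sites.

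**What to change.** 1. Add to 4.2.2 an exclusion along these lines: *current use of clozapine, theophylline, ropinirole, warfarin or methadone, or of an inhibitor or inducer prohibited in Appendix 1, that cannot be safely stopped or switched before the first dose.* Require the check against the Day 0 medication record before randomisation.
2. State in inclusion 5 that contraceptives containing ethinyl estradiol do not qualify.

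Both changes should be carried into the synopsis. The cost is amendment wording and a few otherwise eligible patients screened out, whose drug 6.9.2 already forbids. No new procedure is needed, because current medication is already recorded at Day 0. Section 1 of the SAP records that the study was terminated for futility, so the edit can no longer protect patients in this trial; its use is in any later protocol built on this one.

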7. STUDY COMPLETION

7.1. Patient Completion

Treatment with ABX464/Placebo shall continue until D28, except if a patient fulfils a premature discontinuation criterion (defined below).

Patients should be instructed to take their last study drug dose until the day before D28 visit. Should a patient start to take the treatment at D1, s/he will be instructed to take the last dose on D28.

After D28, patients will come back 21 days after the last study drug intake to perform an onsite safety follow-up visit at D48.

Following this visit, long-term follow-up for respiratory function exploration will be performed on-site for patients having been hospitalized during the study. This follow-up will take place 3 months after the last study drug intake.

For outpatients, a remote telephone follow-up will be performed 3 months after the last study drug intake.

Then, patients will exit the study and will be treated/follow-up according to the site standard of care.

Given the fact that the pulmonary function follow-up is exploratory and depends on the patient status during the study, a patient status is COMPLETE when the treatment period of 28 days is fulfilled, and the safety follow-up of 21 days is performed.

7.2. Patient Premature trial discontinuation

A patient can be withdrawn at any time from the study. Premature trial discontinuation could occur for the following reasons:

- Investigator's decision.
- An Adverse Event or an intercurrent condition that preclude continuation of treatment. Specifically, an elevation $\geq 3.0 \times$ ULN in liver transaminases (AST/SGOT and/or ALT/SGPT) or Alkaline phosphatase or in total bilirubin compared to baseline requires close observation with repeating liver enzymes and serum bilirubin tests every 2 days. Discontinuation of the study treatment should occur if:
 - ALT or AST $> 8 \times$ ULN
 - ALT or AST $> 3 \times$ ULN and total bilirubin $> 2 \times$ ULN or INR > 1.5
 - ALT or AST $> 3 \times$ ULN with appearance of fatigue, nausea, vomiting, right upper quadrant pain or tenderness, fever, rash, and/or eosinophilia ($> 5\%$).
 - Alkaline Phosphatase $\geq 2.0 \times$ ULN
- Serious adverse event with suspected causal relationship to the IMP
- Any relevant toxicity or negative change in the risk/benefit assessment leading to an unacceptable risk for the patient (i.e. occurrence of adverse events which character, severity or frequency is new in comparison to the existing risk profile), or any data deriving from other clinical trials or toxicological studies which negatively influence the risk/benefit assessment.
- Major protocol violation.
- Withdrawal of consent.
- Administrative reasons from Sponsor.

A patient who prematurely exits the study will not be replaced.

All patients, regardless of the completion or premature discontinuation, should come back for an on-site safety follow-up visit 21 days after the last study drug intake, and all examinations must be performed according to the study flow-chart.

The same long-term follow-up will be performed as described in section 7.1 providing the reason for premature discontinuation is not "withdrawal of consent".

7.3. Baseline Failures

A patient who does not fulfil the randomization criteria will be considered as baseline failure. All patient data should be entered in the eCRF including the failure data. Based on the investigator evaluation and sponsor prior approval, a non-randomized patient case can be re-evaluated for randomization. This re-procedure should be documented, the patient should consent again and a new unique and incremental patient Identification (ID) number be allocated.

All potential patients who are assessed for enrolment in this study will be listed on the patient Log/Identification List. Reasons for exclusion will be recorded for potential patients who do not enter the study.

